14.8.2 ECG

QT interval data will be presented using Fridericia's (QTcF) corrections.

ECG variables will be summarised by treatment and time point. Differences from baseline (Day 0, predose) will be summarised by treatment and time point.

Plots of individual QTcF against time will be presented for both absolute values and change from baseline by actual treatment.

The number of patients with a potentially clinically important QTcF value will be summarised by actual treatment and time point, giving the numbers of patients with QTcF > 450 msec, > 480 msec and > 500 msec, and the numbers of patients with increases in QTcF from baseline of > 30 msec and > 60 msec³. A supporting listing of all patients with a QTcF value of PCI and a separate listing of ECG findings classified as abnormal by the investigator will also be provided.

The frequency of clinically significant ECG values will be summarised.

14.8.3 Physical examination and cardiac telemetry findings

Abnormal physical examination findings and cardiac telemetry abnormality findings will be listed. Frequencies of clinically significant postpose physical examinations and cardiac telemetry abnormality will be summarised.

14.8.4 Nasal site and throat examination

Abnormal nasal site and throat findings will be listed.

14.8.5 Columbia-Suicide Severity Rating Scale (C-SSRS)

Positive C-SSRS data defined as patients who answered “Yes” to any question will be listed.

14.8.6 Readiness for discharge questionnaire (RDQ)

RDQ data will be listed. Time to discharge calculated from the end time and defined as time when all criteria are met will be calculated for each patient and the mean, median, minimum and maximum calculated by treatment. If end time is missing then it will be imputed with start time.

14.8.7 Reactivation questionnaire (ReAQ)

ReAQ data will be listed. Occurrence (No/Yes), frequency (when the first re-activation took place, number of days after dosing day of first occurrence and number of re-experience or re-activation events in total after dosing), emotional valence (mostly positive, neutral and mostly negative), functional impact (none, mild, moderate and severe for domains; work, social life and family life) and narrative of potential reactivation will be summarised where applicable by treatment and timepoint.

15 Pharmacokinetic analyses

PK concentration data will be summarised using the PK concentration population.

Plasma concentrations of 5-MeO-DMT and its metabolites (bufotenine, 5-methoxyindolacetic acid (5-MIAA) and 5-MeO-DMT-N-Oxide) will be listed and summarised, by treatment, using descriptive statistics. Individual and mean plasma concentration–time profiles will be presented graphically.

For all variables, N (number of patients receiving the treatment in the population), n (number of observations), arithmetic mean, median, minimum, maximum, SD, %CV, and the 95% CI for the arithmetic mean will be provided.

The between-patient CV will be calculated using:

1. $\%CV_b = 100 * (SD/mean)$ with SD and mean of untransformed data

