1.4.2.2. Clinical Experience with BPL-002

BPL-5MEO-101 (5-MeO-DMT intranasal liquid): Phase 1 placebo-controlled, single-ascending dose study in healthy, psychedelic-naïve subjects (UK) – clinical conduct complete. A total of 24 healthy subjects received single doses of up to 14 mg of BPL-002 (5-MeO-DMT-HCl) and 12 received placebo. No serious adverse events (SAEs) were reported, and all treatment-emergent adverse events (TEAEs) were mild (84%) or moderate (16%). The most frequently reported events were blood pressure systolic increased (15.7%), throat irritation (14.5%) and heart rate increased (8.4%). Overall, the tolerability of up to 14 mg of BPL-002 was considered good by the Safety Review Committee (SRC). The PK of BPL-002 was not linear; exposure did not increase with dose. The highest C_{max} measured in any subject was 13.9 ng/ml and the geometric mean C_{max} of the highest dose group (14 mg) was 2.49 ng/ml.

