The active metabolite, bufotenine, was only detected at very low levels (1.46ng/mL), at the 6 mg dose level 16 min timepoint in one study participant.

In this study assessments were made of PD endpoints that were thought to be predictive of efficacy outcomes in TRD subjects. Literature data indicate that the 30-item Mystical Experience Questionnaire (MEQ-30) data may be used as a surrogate marker of potential future psychiatric efficacy ([Hirschfield, 2021](#); [Griffiths, 2011](#)), and so was the key PD outcome measure conducted. A score of ≥ 3 was defined to be the threshold to elicit a significant experience. A score of ≥ 3 in all 4 subdomains of the MEQ-30 was defined as a complete mystical experience (Barrett, 2015).

The mean subject MEQ-30 scores generally increased with BPL-003 dose, with levels ≥ 3 being observed at doses of 6 mg and above in at least one sub-domain or total MEQ-30 score. The highest MEQ-30 scores were attained with 12 mg BPL-003, and 3 of 5 subjects (60%) achieved a complete mystical experience at 10 mg and 12 mg doses.

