15.1 Pharmacokinetic concentration data

Plasma concentrations of 5-MeO-DMT and its metabolites (bufotenine, 5-methoxyindolacetic acid (5-MIAA) and 5-MeO-DMT-N-Oxide) will be listed and summarised by treatment.

Using actual sample times, linear and semi-logarithmic concentration-time plots of each patient will be prepared. The same linear and logarithmic scales will be used for each patient. The linear and semi logarithmic plots for a given patient will be presented on the same page. For clarity in presentation, individual profiles for different analytes will be separate.

Nominal blood sampling times will be used to calculate the mean (SD) drug concentrations at each time point. Comparative linear and semi logarithmic plots of the mean (\pm SD) concentration-time data for each group will be prepared.

For individual concentration–time plots, plasma concentrations below the limit of quantification of the assay (BLQ) will be treated as follows: values that occur before t_{max} will be taken as zero; all other values will be taken as missing.

For calculation of plasma concentration summary statistics, BLQ values will be taken as zero, unless they fall between two quantifiable concentrations, in which case they will be treated as missing.

16 Pharmacodynamic analyses

PD data will be summarised using the ITT and PP (alcohol use from the TLFB interview, and MEQ only) Population.

PD data will be listed by treatment and time point and summarised by treatment and time point. Changes from baseline questionnaires will be summarised by time point and treatment.

The PD data includes the following psychometric scales and questionnaires: Stanford Expectation of Treatment Scale (SETS), Mystical Experience Questionnaire (MEQ-30), Ego Dissolution Inventory (EDI), 5-Level EuroQol 5-Dimension (EQ-5D-5L), Timeline Follow-Back (TLFB), Montgomery-Åsberg Depression Rating Scale (MADRS), Alcohol Craving Questionnaire (ACQ), Craving Visual Analogue Scale (VAS), Clinical Global Impression of Severity (CGI-S), Patient Global Impression of Change (PGIC), Clinical Institute Withdrawal Assessment for Alcohol-Revised (CIWA-Ar), Short Inventory of Problems (SIP).

Each psychometric scale/questionnaire will be reported using standard scales as described in Appendix A: Pharmacodynamic analysis.

The scales will be listed and summarised.

In addition, an individual plot of the mean units of alcohol per day (UPD) from the TLFB questionnaire will be produced.

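### The planned mean, %CV, 95% CI and mean ± SD semi-log plots do not work for an analyte that is mostly below the limit of quantification, as bufotenine very probably will be.

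*SAP*

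**What the plan says.** SAP section 15 covers 5-MeO-DMT, bufotenine, 5-MIAA and 5-MeO-DMT-N-oxide. For every variable it asks for counts, the arithmetic mean with its SD and %CV, and the median and range, and it says that "the 95% CI for the arithmetic mean will be provided". The between-patient CV is calculated "with SD and mean of untransformed data". No geometric mean is planned, and no minimum number of quantifiable values is set.

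For summary statistics, section 15.1 says that "BLQ values will be taken as zero, unless they fall between two quantifiable concentrations, in which case they will be treated as missing". It also asks for "Comparative linear and semi logarithmic plots of the mean" with SD bars for each group.

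The shells apply this to all four analytes alike. T_PK1 has columns for the mean, 95% CI, SD, %CV, median, minimum and maximum, and a count of imputed values. F_PK2 is used for the mean ± SD and the mean-only figures, on linear and semi-log axes, and its footnote says that BLQ values become zero. The bufotenine outputs are Table 14.2.1.2 and Figures 14.2.2.1 to 14.2.2.3.

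Protocol section 8 sets three samples, at 5, 15 and 60 minutes. Up to 12 patients are planned.

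**The concern.** The protocol's own data suggest that bufotenine will be mostly or wholly unquantifiable. In Part A of BPL-003-103 it was detected "at very low levels (1.46ng/mL), at the 6 mg dose level 16 min timepoint in one study participant", and 31 subjects in that part received active drug. With zeros substituted, a table row is then built from a column of zeros, or from zeros and one to three positive values. A mean with a symmetric interval is not a meaningful summary of such data, and the matching semi-log figure cannot be drawn.

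Bufotenine is not incidental. Protocol section 1.4.1.2 describes it as an active, potent psychedelic metabolite, and the PK endpoint names it. Exploring exposure in patients with AUD is an exploratory objective, and these tables and figures are its planned output. At stake is whether the bufotenine output is readable: a CI of (0, 0) suggests that exposure is known to be exactly zero, and a negative limit is physically impossible.

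**Working it through.** The documents give no PK interval, coverage or CV for BPL-003, so there is no figure to reproduce.

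**Inputs.** n = 12 (protocol 11.2, upper limit); bufotenine value x = 1.46 ng/mL and one detection in 31 (protocol 1.4.2.3.1); BLQ = 0 (SAP 15.1). The SAP gives no CI formula, so I use the usual one, mean ± t × SD/√n, with t(0.975, 11) = 2.201.

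**Step 1. Interval when k of 12 are quantifiable.** Assume equal values x and the rest zero. With p = k/n, mean = p·x and SD = x·√[p(1 − p)·n/(n − 1)].

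| k of 12 | Mean | SD | 95% CI (ng/mL) | Mean − SD |
|---|---|---|---|---|
| 0 | 0 | 0 | 0 to 0 (%CV = 0/0) | 0 |
| 1 | 0.122 | 0.421 | −0.146 to 0.389 | −0.30 |
| 2 | 0.243 | 0.568 | −0.118 to 0.604 | −0.33 |
| 3 | 0.365 | 0.660 | −0.055 to 0.785 | −0.30 |
| 4 | 0.487 | 0.719 | 0.030 to 0.943 | −0.23 |
| 6 | 0.730 | 0.762 | 0.246 to 1.214 | −0.03 |
| 7 | 0.852 | 0.752 | 0.374 to 1.329 | 0.10 |

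With exactly one quantifiable value the lower limit is (x/n)(1 − t), here 0.1217 × (1 − 2.201) = −0.146. It is negative at any n, because t exceeds 1. In general the limit is negative when CV > √n/t, which is 157% at n = 12 and 95% at n = 6. At n = 6 it is negative for 1 to 3 quantifiable values (−0.382, −0.305, −0.109). The lower SD bar is at or below zero for 0 to 6 of 12.

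**Step 2. How likely these outcomes are.** Take 1/31 as an illustrative rate.

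- None of 12: (30/31)^12 = 0.675.
- One: 12 × (1/30) × 0.675 = 0.270. Two: 66 × (1/30)² × 0.675 = 0.049. Three: 220 × (1/30)³ × 0.675 = 0.005. Sum for one to three: about 0.325.
- Together: more than 99.9%.

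The rate is uncertain. The single detection was at 6 mg, none is reported at 10 or 12 mg, and the count is per participant rather than per time point. All of this makes the all-BLQ result more likely. In the other direction, at an assumed 10% rate, none of 12 has probability 0.9^12 = 0.28, and one to three has 0.377 + 0.230 + 0.085 = 0.69. The total is still about 97%.

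**Step 3. A well-quantified analyte (secondary).** Coverage of the nominal 95% t interval for the arithmetic mean was simulated with lognormal data, 200,000 samples per setting. The CVs are assumed.

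| CV | n = 12 | n = 6 |
|---|---|---|
| 30% | 94.1% | 93.8% |
| 50% | 92.7% | 92.1% |
| 70% | 90.7% | 89.7% |
| 100% | 87.8% | 86.1% |
| 150% | 82.9% | 80.3% |

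A back-transformed log-scale interval covers the geometric mean at 95.0% to 95.1% throughout. It cannot be computed if any value is zero.

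**The case against.** The best defence is that the reader will not be misled. The median, minimum and maximum are planned, T_PK1 counts imputed values, listings show BLQ as BLQ, individual plots are planned, and each analyte also has a mean figure without SD bars. SAP 11.2 presents confidence intervals in general only where they help interpretation. PK is exploratory, no hypothesis is tested, and no decision uses this interval. All of this stands, and it makes the point minor. It does not remove it. Section 15 asks for the interval for every variable, and dropping the SD bars does not help when the mean itself is zero on a log axis.

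A reader might infer several stronger points that the documents do not support.

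- **That the tables will show negative concentrations.** A confidence limit is not a concentration, and the negative limit is conditional. All values BLQ is the more likely outcome at 1/31.
- **That the parent drug is strongly skewed.** Protocol 1.4.2.2 gives a highest individual Cmax of 13.9 ng/mL and says that the geometric mean "of the highest dose group (14 mg) was 2.49 ng/ml". Those data are for BPL-002, another formulation, and the dose group of the 13.9 value is not stated, so the comparison may mix doses.
- **That geometric means would allow comparison with that figure.** It is a Cmax. This SAP summarises concentrations at three times and derives no Cmax.
- **That the interval affects dose escalation.** The safety committee meets only if triggered and reviews data from at least 3 patients. The final table comes after database lock.
- **That a geometric interval cures the tendency to miss high.** It targets a smaller quantity. At n = 12 its upper limit lies below the true arithmetic mean in 14%, 20% and 26% of samples at CV 60%, 80% and 100%, against 7.7%, 9.9% and 12.0% for the planned interval.

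**Conclusion.** The point holds for analytes that are mostly BLQ, and it is minor. For bufotenine with 12 patients, the planned statistics are either degenerate (CI 0 to 0, %CV undefined) or have a negative lower limit in nearly every likely outcome. The semi-log mean ± SD plot cannot be drawn as specified in either case. This rests on the usual t interval, equal quantifiable values of 1.46 ng/mL, n = 12 at each time point, and a detection rate near 1/31; at 10% the conclusion is little changed. With unequal values the limit could also be negative at 4 of 12.

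For 5-MeO-DMT, the arithmetic interval loses about 1 percentage point of coverage at CV 30% and about 7 at CV 100% (n = 12). Since the documents give no CV for BPL-003, this supports adding geometric statistics but does not show that the arithmetic mean is wrong. Choosing between the two as the main summary is largely preference.

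**What to change.** In SAP 15 and 15.1, T_PK1 and F_PK2:

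- Add n (%) above the lower limit of quantification for each analyte and time point.
- Where more than half the values at a time point are BLQ, report only that n (%), the median and the maximum, with no mean, CI, %CV or SD bars. Setting the cut-off at half or more would also catch the boundary cases above (6 of 12 for the SD bar, 3 of 6 for the CI).
- For analytes that are fully or nearly fully quantifiable, add the geometric mean, geometric CV and back-transformed 95% CI beside the arithmetic statistics. State how BLQ values are handled on the log scale, because zeros cannot be logged.
- On semi-log plots use the geometric mean with geometric SD bars. Where the BLQ rule applies, rely on the individual plots.

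The cost is a few lines of SAP text and changes to two shells. No new samples or data are needed.

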15.1 Pharmacokinetic concentration data

Plasma concentrations of 5-MeO-DMT and its metabolites (bufotenine, 5-methoxyindolacetic acid (5-MIAA) and 5-MeO-DMT-N-Oxide) will be listed and summarised by treatment.

Using actual sample times, linear and semi-logarithmic concentration-time plots of each patient will be prepared. The same linear and logarithmic scales will be used for each patient. The linear and semi logarithmic plots for a given patient will be presented on the same page. For clarity in presentation, individual profiles for different analytes will be separate.

Nominal blood sampling times will be used to calculate the mean (SD) drug concentrations at each time point. Comparative linear and semi logarithmic plots of the mean (\pm SD) concentration-time data for each group will be prepared.

For individual concentration–time plots, plasma concentrations below the limit of quantification of the assay (BLQ) will be treated as follows: values that occur before t_{max} will be taken as zero; all other values will be taken as missing.

For calculation of plasma concentration summary statistics, BLQ values will be taken as zero, unless they fall between two quantifiable concentrations, in which case they will be treated as missing.

16 Pharmacodynamic analyses

PD data will be summarised using the ITT and PP (alcohol use from the TLFB interview, and MEQ only) Population.

PD data will be listed by treatment and time point and summarised by treatment and time point. Changes from baseline questionnaires will be summarised by time point and treatment.

The PD data includes the following psychometric scales and questionnaires: Stanford Expectation of Treatment Scale (SETS), Mystical Experience Questionnaire (MEQ-30), Ego Dissolution Inventory (EDI), 5-Level EuroQol 5-Dimension (EQ-5D-5L), Timeline Follow-Back (TLFB), Montgomery-Åsberg Depression Rating Scale (MADRS), Alcohol Craving Questionnaire (ACQ), Craving Visual Analogue Scale (VAS), Clinical Global Impression of Severity (CGI-S), Patient Global Impression of Change (PGIC), Clinical Institute Withdrawal Assessment for Alcohol-Revised (CIWA-Ar), Short Inventory of Problems (SIP).

Each psychometric scale/questionnaire will be reported using standard scales as described in Appendix A: Pharmacodynamic analysis.

The scales will be listed and summarised.

In addition, an individual plot of the mean units of alcohol per day (UPD) from the TLFB questionnaire will be produced.

17 Changes from the protocol specified statistical analysis

After the study was submitted to the Medicines and Healthcare products Regulatory Agency (MHRA) and ethics committee the following changes were made to the analyses:

- Double flagged laboratory values have been updated to report only out of range values

18 References

1. International Conference on Harmonization, 1998. Statistical Principles for Clinical Trials – ICH Harmonised Tripartite Guideline. Guidance for Industry, E9, FDA federal register, Vol 63, 1998, p49583. Available at: <http://www.fda.gov/cder/guidance>.
2. International Conference on Harmonization, 1995. Structure and Content of Clinical Study Reports – ICH Harmonised Tripartite Guideline. Guidance for Industry, E3, FDA federal register, Vol 61, 1996, p37320. Available at: <http://www.fda.gov/cder/guidance>.
3. International Conference on Harmonisation, 2005. Clinical Evaluation of QT/QTc Interval Prolongation and Proarrhythmic Potential for Non-Antiarrhythmic Drugs. Concept paper, Guidance for Industry, E14, Center for Drug Evaluation and Research (CDER). Available at: <http://www.fda.gov/cder/guidance/6922fnl.htm>.
4. Julious, SA & Debnarot, CAM (2000) “Why are Pharmacokinetic Data Summarised by Arithmetic Means?”, Journal of Biopharmaceutical Statistics, 10 (1), p55-71

19 ATTACHMENTS

19.1 Table of contents for data display specifications

For overall page layout refer to Appendix B: Sample page .

The numbering in the tables below will take precedence over the numbering in the shells.

The following tables and figures will be produced (templates provided in Section 19.2.1 and 19.2.2):

Table	Description	Population	Source Listing	Template (Shells below)
10.1	Summary of patient disposition	Safety	16.2.1.2, 16.2.1.3, 16.2.3.1	T_SD1
14.1	DEMOGRAPHIC DATA			
14.1.1	Summary of demographic characteristics	Safety	16.2.4.1	T_DM1
14.1.2	Summary of alcohol and drug abuse use data	Safety	16.2.4.4, 16.2.4.5	T_AUDU
14.2	PHARMACOKINETIC AND PHARMACODYNAMIC DATA			
14.2.1.1	Summary of 5MeO-DMT plasma pharmacokinetic concentration-time data [units]	PK Concentration	16.2.6.1	T_PK1
14.2.1.2	Summary of bufotenine plasma pharmacokinetic concentration-time data [units]	PK Concentration	16.2.6.1	T_PK1
14.2.1.3	Summary of 5-methoxyindolacetic acid plasma pharmacokinetic concentration-time data by treatment group [units]	PK Concentration	16.2.6.1	T_PK1
14.2.1.4	Summary of 5-MeO-DMT-N-Oxide plasma pharmacokinetic concentration-time data by treatment group [units]	PK Concentration	16.2.6.1	T_PK1
14.2.2	Summary of Stanford Expectation of Treatment Scale (SETS)	ITT	16.2.6.2	T_PD1
14.2.3.1	Summary of Mystical Experience Questionnaire (MEQ-30) [intent-to-treat population]	ITT	16.2.6.3	T_PD1
14.2.3.2	Summary of Mystical Experience Questionnaire (MEQ-30) [per protocol population]	PP	16.2.6.3	T_PD1
14.2.3.3	Summary of complete mystical experience [intent-to-treat population]	ITT	16.2.6.3	T_PD3
14.2.3.4	Summary of complete mystical experience [per protocol population]	PP	16.2.6.3	T_PD3
14.2.4	Summary of Ego Dissolution Inventory (EDI)	ITT	16.2.6.4	T_PD1
14.2.5	Summary of 5-Level EuroQol 5-Dimension (EQ-5D-5L)	ITT	16.2.6.5	T_PD4
14.2.6.1	Summary of Timeline Follow-Back (TLFB)) [intent-to-treat population]	ITT	16.2.6.6	T_PD1a
14.2.6.2	Summary of Timeline Follow-Back (TLFB) [per protocol population]	PP	16.2.6.6	T_PD1a
14.2.7.1	Summary of Montgomery-Åsberg Depression Rating Scale (MADRS)	ITT	16.2.6.7	T_PD2

Table	Description	Population	Source Listing	Template (Shells below)
14.2.7.2	Summary of patients with 50% reduction from baseline of MADRS scores	ITT	16.2.6.7	T_PD2a
14.2.7.3	Summary of patients in remission based on MADRS scores ≤ 10	ITT	16.2.6.7	T_PD2b
14.2.8	Summary of Alcohol Craving Questionnaire (ACQ)	ITT	16.2.6.8	T_PD2
14.2.9	Summary of Craving Visual Analogue Scale (VAS)	ITT	16.2.6.9	T_PD1
14.2.10	Summary of Clinical Global Impression of Severity (CGI-S)	ITT	16.2.6.10	T_PD6
14.2.11	Summary of Patient Global Impression of Change (PGIC)	ITT	16.2.6.11	T_PD6
14.2.12	Summary of Clinical Institute Withdrawal Assessment for Alcohol-Revised (CIWA-Ar)	ITT	16.2.6.12	T_PD1
14.2.13	Summary of Short Inventory of Problems (SIP)	ITT	16.2.6.13	T_PD2
14.3	SAFETY DATA			
14.3.1.1	Overall summary of treatment-emergent adverse events	Safety	16.2.7.1	T_AE2
14.3.1.2	Summary of treatment-emergent adverse events	Safety	16.2.7.1	T_AE1
14.3.1.3	Summary of drug-related treatment-emergent adverse events	Safety	16.2.7.1	T_AE1
14.3.1.4	Summary of treatment-emergent adverse events by maximum severity	Safety	16.2.7.1	T_AE3
14.3.1.5	Summary of treatment-emergent adverse events by day of onset	Safety	16.2.7.1	T_AE4
14.3.2.1	Listing of fatal adverse events	Safety	16.2.7.1	L_AE1_PG
14.3.2.2	Listing of non-fatal serious adverse events	Safety	16.2.7.1	L_AE1_PG
14.3.2.3	Listing of other significant adverse events	Safety	16.2.7.1	L_AE1_PG
14.3.3	Narratives of deaths, other serious and significant adverse events	Safety		-
14.3.4.1	Summary of post dose clinically significant abnormal laboratory values by treatment and planned relative time	Safety	16.2.8.1, 16.2.8.3, 16.2.8.5	T_LB4
14.3.4.2	Summary of post dose clinically significant abnormal alcohol biomarker values by treatment and planned relative time	Safety	16.2.8.7	T_LB4
14.3.5.1	Summary of chemistry laboratory values	Safety	16.4	T_LB2
14.3.5.2	Summary of haematology laboratory values	Safety	16.4	T_LB2
14.3.5.3	Summary of coagulation laboratory values	Safety	16.4	T_LB2
14.3.5.4	Summary of alcohol biomarker data	Safety	16.4	T_LB2

Table	Description	Population	Source Listing	Template (Shells below)
14.3.6.1	Summary of vital signs	Safety	16.4	T_VS1
14.3.6.2	Summary of vital signs of potential clinical importance by treatment, planned relative time and parameter	Safety	16.2.9.1	T_VS2
14.3.6.3	Summary of vital signs of potential clinical importance by parameter and treatment (excluding baseline time point)	Safety	16.2.9.1	T_VS3
14.3.6.4	Summary of post dose clinically significant vital signs	Safety	16.2.9.2	T_VS4
14.3.6.5	Summary of peak vital signs ranges by treatment, ranges and parameter – Day 0 post dose	Safety	16.2.9.3	T_VS5
14.3.6.6	Summary of peak vital signs by treatment and parameter - baseline and day 0 post dose	Safety	16.2.9.3	T_VS6
14.3.7.1	Summary of ECG values	Safety	16.4	T_EG2
14.3.7.2	Summary of QTcF values and changes in QTcF values of potential clinical importance by treatment, planned relative time and category	Safety	16.2.9.4	T_EG3
14.3.7.3	Summary of post dose clinically significant ECG values	Safety	16.2.9.5	T_EG5
14.3.7.4	Summary of post dose clinically significant cardiac telemetry abnormalities	Safety	16.2.9.6	T_EG5
14.3.7.5	Summary of post dose clinically significant physical examination findings	Safety	16.2.9.7	T_EG5
14.3.7.6	Summary of post dose clinically significant nasal site and throat reaction findings	Safety	16.2.9.8	T_EG5
14.3.7.7	Summary of readiness of discharge questionnaire (RDQ)-Time to discharge (units)	Safety	16.2.9.10	T_RDQ
14.3.7.8	Summary of re-activation questionnaire (ReAQ)	Safety	16.2.9.11	T_ReAQ

Figure	Description	Population	Source Listing	Template (Shells below)
14.2	PHARMACOKINETIC AND PHARMACODYNAMIC DATA			
14.2.1.1	Individual 5MeO-DMT plasma concentration-time plots (linear and semi-log)	PK Concentration	16.2.6.1	F_PK1
14.2.1.2	Mean (+/- SD) 5MeO-DMT plasma concentration-time plots (linear and semi-log)	PK Concentration	16.2.6.1	F_PK2
14.2.1.3	Mean 5-MeO-DMT plasma concentration-time plots (linear and semi-log)	PK Concentration	16.2.6.1	F_PK2
14.2.2.1	Individual bufotenine plasma concentration-time plots (linear and semi-log)	PK Concentration	16.2.6.1	F_PK1
14.2.2.2	Mean (+/- SD) bufotenine plasma concentration-time plots (linear and semi-log)	PK Concentration	16.2.6.1	F_PK2
14.2.2.3	Mean bufotenine plasma concentration-time plots (linear and semi-log)	PK Concentration	16.2.6.1	F_PK2
14.2.3.1	Individual 5-methoxyindolacetic acid plasma concentration-time plots (linear and semi-log)	PK Concentration	16.2.6.1	F_PK1
14.2.3.2	Mean (+/- SD) 5-methoxyindolacetic acid plasma concentration-time plots (linear and semi-log)	PK Concentration	16.2.6.1	F_PK2
14.2.3.3	Mean 5-methoxyindolacetic acid plasma concentration-time plots (linear and semi-log)	PK Concentration	16.2.6.1	F_PK2
14.2.4.1	Individual 5-MeO-DMT-N-Oxide plasma concentration-time plots (linear and semi-log)	PK Concentration	16.2.6.1	F_PK1
14.2.4.2	Mean (+/- SD) 5-MeO-DMT-N-Oxide plasma concentration-time plots (linear and semi-log)	PK Concentration	16.2.6.1	F_PK2
14.2.4.3	Mean 5-MeO-DMT-N-Oxide plasma concentration-time plots (linear and semi-log)	PK Concentration	16.2.6.1	F_PK2
14.2.5.1	Individual mean units of alcohol per day (UPD)-time plots [intent-to-treat population]	ITT	16.2.6.6	F_PD
14.2.5.2	Individual mean units of alcohol per day (UPD)-time plots [per protocol population]	PP	16.2.6.6	F_PD
14.3	SAFETY DATA			

14.3.1	Individual systolic blood pressure-time plots	Safety	16.4	F SAF1
14.3.2	Individual diastolic blood pressure-time plots	Safety	16.4	F SAF1
14.3.3	Individual heart rate-time plots	Safety	16.4	F SAF1
14.3.4	Individual QTcF-time plots	Safety	16.4	F SAF1

The following abbreviated listings will be produced (templates provided in Section 19.2.3):

Listing	Description	Template (Shells below)
16.2.1	Study dates & disposition of patients	
16.2.1.1	Listing of study dates	L SD1 PG
16.2.1.2	Listing of reasons for withdrawal	L SD2 PG
16.2.1.3	Listing of patients screened but not enrolled	L SD3 PG
16.2.2	Protocol deviations	
16.2.2.1	Listing of patients with time deviations	L TD1 PG
16.2.2.2	Listing of patients with minor protocol deviations	L DV2 PG
16.2.2.3	Listing of patients with major protocol deviations	L DV2 PG
16.2.3	Analysis sets, including patients excluded from analysis	
16.2.3.1	Listing of analysis populations	L AN1 PG
16.2.4	Demographic data & concomitant medication	
16.2.4.1	Listing of demographic characteristics	L DM1 PG
16.2.4.2	Listing of concomitant medications	L CM1 PG
16.2.4.3	Listing of medical history	L MH1 PG
16.2.4.4	Listing of alcohol use history	L AUH PG
16.2.4.5	Listing of drug abuse use history	L DUH PG
16.2.5	Study drug administration	
16.2.5.1	Listing of exposure data	L EX1 PG
16.2.6	Pharmacokinetic and Pharmacodynamic data	
16.2.6.1	Listing of 5MeO-DMT, bufotenine, 5-methoxyindolacetic acid and 5-MeO-DMT-N-Oxide plasma pharmacokinetic concentration-time data	L PK1 PG
16.2.6.2	Listing of Stanford Expectation of Treatment Scale (SETS)	L PD4 PG

Listing	Description	Template (Shells below)
16.2.6.3	Listing of Mystical Experience Questionnaire (MEQ-30)	L_PD2_PG
16.2.6.4	Listing of Ego Dissolution Inventory (EDI)	L_PD3_PG
16.2.6.5	Listing of 5-Level EuroQol 5-Dimension (EQ-5D-5L)	L_PD5_PG
16.2.6.6	Listing of Timeline Follow-Back (TLFB)	L_PD6_PG
16.2.6.7	Listing of Montgomery-Åsberg Depression Rating Scale (MADRS)	L_PD4a_PG
16.2.6.8	Listing of Alcohol Craving Questionnaire (ACQ)	L_PD7_PG
16.2.6.9	Listing of Craving Visual Analogue Scale (VAS)	L_PD3_PG
16.2.6.10	Listing of Clinical Global Impression of Severity (CGI-S)	L_PD8_PG
16.2.6.11	Listing of Patient Global Impression of Change (PGIC)	L_PD8_PG
16.2.6.12	Listing of Clinical Institute Withdrawal Assessment for Alcohol-Revised (CIWA-Ar)	L_PD9_PG
16.2.6.13	Listing of Short Inventory of Problems (SIP)	L_PD2_PG
16.2.7	Adverse events	
16.2.7.1	Listing of all adverse events	L_AE1_PG
16.2.7.2	Listing of serious adverse events	L_AE1_PG
16.2.7.3	Listing of adverse events leading to withdrawal from study	L_AE1_PG
16.2.7.4	Listing of adverse events of special situation (AESS)	L_AE1_PG
16.2.7.5	Listing of adverse events of special interest (AESI)	L_AE1_PG
16.2.8	Laboratory values	
16.2.8.1	Listing of post dose clinically significant abnormal chemistry laboratory values	L_LB1_PG
16.2.8.2	Listing of all clinical chemistry laboratory data for patients with post dose clinically significant abnormal chemistry laboratory values	L_LB1_PG
16.2.8.3	Listing of post dose clinically significant abnormal haematology laboratory values	L_LB1_PG
16.2.8.4	Listing of all haematology laboratory data for patients with post dose clinically significant abnormal haematology laboratory values	L_LB1_PG
16.2.8.5	Listing of post dose clinically significant abnormal coagulation laboratory values	L_LB1_PG
16.2.8.6	Listing of all coagulation laboratory data for patients with post dose clinically significant abnormal coagulation laboratory values	L_LB1_PG
16.2.8.7	Listing of post dose clinically significant abnormal alcohol biomarker values	L_LB1_PG
16.2.8.8	Listing of all alcohol biomarker data for patients with post dose clinically significant abnormal alcohol biomarker values	L_LB1_PG

Listing	Description	Template (Shells below)
16.2.9	Vital signs, ECG variables physical findings nasal site reactions, C-SSRS, RDQ and ReAQ data	
16.2.9.1	Listing of vital signs of potential clinical importance	L VS1 PG
16.2.9.2	Listing of clinically significant vital signs	L VS2 PG
16.2.9.3	Listing of peak vital signs data	L VS3 PG
16.2.9.4	Listing of QTcF values of potential clinical importance	L EG1 PG
16.2.9.5	Listing of abnormal ECG findings	L EG2 PG
16.2.9.6	Listing of abnormal cardiac telemetry findings	L EG3 PG
16.2.9.7	Listing of abnormal physical examination findings	L PE1 PG
16.2.9.8	Listing of abnormal nasal site and throat examination findings	L NSE1 PG
16.2.9.9	Listing of positive Columbia-Suicide Severity Rating Scale (C-SSRS) data	L CSS PG
16.2.9.10	Listing of Readiness of Discharge Questionnaire (RDQ)	L RDQ PG
16.2.9.11	Listing of re-activation questionnaire (ReAQ)	L ReAQ PG

Complete listings of all data collected in this study will also be produced separately.

